10.7.4. Patient Discontinuation from the Study

Patient discontinuation prior to the patient's completion of the study is expected to be uncommon, occurring only if the patient explicitly withdraws consent. At the time of discontinuing from the study, the Medical Monitor should be contacted, and, if possible, an early discontinuation visit should be conducted, per the Study Schedule. The patient will be

permanently discontinued both from the IMP and from the study at that time. During the study closeout period, survival (vital) status will be collected within legal and ethical boundaries for all patients randomized who withdrew their participation from the study.

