4.3. Study Closeout

The study will continue until all the following criteria have been met:

1. at least 1,620 patients have experienced an adjudicated primary 4-component MACE (CV death, nonfatal MI, nonfatal stroke, or coronary revascularization),
2. at least 810 patients have experienced an adjudicated 3-component MACE (CV death, nonfatal MI, or nonfatal stroke) and
3. 24 months have elapsed since the last patient was randomized.

During the study closeout period (when the patients' End of Study (EOS) Visits will be scheduled), each patient still in the study will be required to complete an in-clinic visit which is

designated as the EOS Visit and perform the procedures according to Protocol Appendix 1, Schedule of Events. Patients who are still on IMP at the visit will be asked to end study treatment.

A post-treatment telephone visit will occur 30 days (\pm 10 days) after the EOS visit to assess AEs, SAEs and identify potential clinical endpoints.

[figure not shown]
During the study closeout period, vital status will be collected within legal and ethical boundaries (see Protocol Section 10.7.5) for all patients who did not complete the study, and only those with unknown status are considered as lost to follow-up.

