Date of Last Survival Follow-Up (DLSFU): For patients who completed the study, or withdrew consent, or discontinued study and were identified as dead only through survival search (death is not adjudicated), it is the DSC. For all other patients it is the Date of Last Known Alive. This is the last date for survival status follow-up.

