15.2.3. Primary Efficacy Endpoint Data Censoring Pattern

For patients who were censored, i.e., did not experience MACE-4 endpoint, the pattern of censoring will be summarized by treatment, including

- censored for non-CV death
- censored on or after completion of the EOS visit during closeout
- censored prior to the study closeout period and not by non-CV death
- censored within 30 days of the last dose
- censored more than 30 days after the last dose

The total patient-year lost-to-follow-up will be calculated by treatment group as the sum of time from the date of censoring prior to study closeout and not by non-CV death, to the May 15, 2022 when the study closeout was initiated.

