APPENDIX 6. MULTIPLE IMPUTATION AND TIPPING POINT ANALYSIS

For the primary 4-component MACE endpoint (MACE-4), the multiple imputation and tipping point (TP) analyses are comprised of the following steps:

Step 1. Model for Unobserved Events

A parametric exponential survival model (e.g., PROC LIFEREG in SAS) is used for the events after stopping the assigned treatment. Specifically, when fitting the model, the start time of each patient is the date of the last dose. The event or censoring time remains the same as in the primary analysis. Patients who had events prior to the last dose will not be included in the analysis. Treatment assignment is included as a covariate and the parameters are intercept α , and β which is the log hazard ratio between active treatment and placebo groups after they have stopped the assigned treatment.

Step 2: Simulation of Unobserved Events

For patients who were censored (i.e., did not experience a MACE-4), a time to event is simulated from the fitted model in Step 1, and it is added to the date of last dose for each patient.

Afterwards, all patients are censored at the calendar date of [REDACTED] or their date of non-CV death.

[figure not shown]
- For multiple imputation, the parameters $(\tilde{\alpha}, \tilde{\beta})$ will be drawn from a bivariate normal distribution centered around the MLEs $(\hat{\alpha}, \hat{\beta})$ with the model-based variance-covariance matrix. This is an approximate to the posterior distribution of the parameters when a flat non-informative prior is used.
- For TP, $\hat{\alpha}$ is used. However, instead of the observed treatment effect $\hat{\beta}$, a range of values (from hazard ratios of 1.00 to 1.10 in 0.01 increment) will be used to allow the patients assigned to the active treatment to have the same or event worse outcome than those assigned to the placebo group after dropping out and stopping the treatment.

[figure not shown]
A total of 100 datasets will be simulated for each scenario.

[figure not shown]
Step 3: Fitting Cox PH Model using Simulated Data and Final Inference

[figure not shown]
For each simulated dataset, a Cox PH model is used to estimate the difference (log hazard ratio) between the active treatment and placebo groups.

[figure not shown]
The resulted estimates are combined using Rubin's method (Rubin, 1987), e.g., using PROC MIANALYZE in SAS.

[figure not shown]

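### SAP Appendix 6 does not end simulated MACE follow-up at deaths found only in the closeout vital-status search: a minor gap, cheap to close

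*SAP*

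**What the plan says.** SAP 15.2.4 plans two sensitivity analyses of the primary endpoint, multiple imputation and tipping point, because early censoring may be informative. Appendix 6 gives the steps. For each patient censored without a MACE-4, "a time to event is simulated from the fitted model in Step 1" and added to the date of last dose. After that, "all patients are censored at the calendar date of [REDACTED] or their date of non-CV death". The calendar date is blacked out; the rule about deaths is fully visible.

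At closeout, "vital status will be collected within legal and ethical boundaries (see Protocol Section 10.7.5) for all patients who did not complete the study" (SAP 4.3). Protocol 10.7.4 says the same of withdrawals: "survival (vital) status will be collected within legal and ethical boundaries for all patients randomized who withdrew their participation from the study".

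SAP 7.2.1, under the date of last survival follow-up, recognises patients who "discontinued study and were identified as dead only through survival search (death is not adjudicated), it is the DSC", the date of study completion. SAP 15.1 takes the CV or non-CV classification of deaths from the Clinical Event Committee.

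SAP 15.2.3 adds a descriptive total: "The total patient-year lost-to-follow-up will be calculated by treatment group as the sum of time from the date of censoring prior to study closeout", leaving out patients censored by a non-CV death and running to the date closeout began.

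**The concern.** A death found only in the search has no adjudicated cause. It is therefore neither a CV death, which would be a MACE-4, nor a non-CV death, which would end follow-up in Step 2. A programmer who follows Step 2 exactly would keep a patient with a known death date at risk until the calendar cut-off and could assign that patient a MACE after death. The death itself, which may have been cardiovascular, plays no part.

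These two analyses exist to test whether dropout is informative. Death after dropout is the most informative outcome the trial collects on patients who left. If such deaths differed between arms, neither the imputation nor the tipping-point result would show it.

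**Working it through.** **1. Does another rule close the gap?**

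| Place | Rule | Covers search-only deaths? |
|---|---|---|
| SAP 7.2.1, date of last assessment | Date of death is used if the patient died during the study within 90 days of the last visit | No. SAP 7.1 takes death during the study to mean the patient had not discontinued before death |
| Protocol 13.2.6 | Deaths on study or within 30 days after discontinuation or completion go to adjudication | No. It leaves the later deaths |
| Protocol 15.6 | After loss or withdrawal, a later-known death sets the censoring date | Non-CV deaths only, and for the primary analysis only. Under Protocol 15.1 the SAP prevails on analysis |
| SAP 15.2.3 | Lost time excludes censoring by non-CV death | No. Same exception, same gap |

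No visible rule treats an unadjudicated death as non-CV or as a stop in Step 2.

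**2. The plan's own figures.** SAP 8.1 gives HR 0.85, at least 90% power, alpha 0.05 and 1,620 events; the test is two-sided (Protocol synopsis).

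- Events = 4(1.960 + 1.282)² / (ln 0.85)² = 1,592 (Schoenfeld); Freedman's formula gives 1,599. Both are within 3% of 1,620.
- Power at 1,620 events = Φ(½·√1620·0.1625 − 1.960) = Φ(1.31) = 90.5%.

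These reproduce. The documents give no figure for search-only deaths, so what follows is an illustration.

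**3. Inputs to the illustration.**

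- From the plan: 14,000 patients, 1:1; enrolment over 33 months and closeout 24 months after last entry, so 24 to 57 months of follow-up; placebo rate 3.59% per year, hazard −ln(1 − 0.0359) = 0.0366; HR 0.85.
- Assumed: dropout from the study of 1, 3 or 5% per year; mortality after dropout of 2, 5 or 10% per year, equal in both arms; every such death traced and unadjudicated; last dose on the day of leaving. Simulated MACE use the placebo hazard, times 1.00 or 1.10 on active (the ends of the tipping-point range).
- 40 simulated trials per scenario. About 1,500 events occur per trial, fewer than 1,620 because follow-up is stopped at the 24-month minimum.

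**4. Hand check (1% dropout, 2% mortality).** Follow-up F is uniform from 2 to 4.75 years: mean 3.375, variance 2.75²/12 = 0.630, so E[F²] = 12.02. Mean time from leaving to closeout is about 12.02 / (2 × 3.375) = 1.78 years. With about 440 event-free leavers, deaths ≈ 440 × 1.78 × 0.02 = 15.7; the simulation gives about 16. Simulated MACE after death ≈ 18 patient-years × 0.0366 = 0.7; the simulation gives 0.5–0.9.

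**5. Results** (ranges span the two active-arm multipliers; HR changes are means against the literal Step 2).

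| Dropout / mortality per year | Leavers | Dead by closeout | Patient-years after death | Simulated MACE after death | HR change, stop at any death | HR change, deaths counted as MACE-4 |
|---|---|---|---|---|---|---|
| 1% / 2% | 440–444 | 16 | 18–19 | 0.5–0.9 | −0.0002 to −0.0001 | +0.0009 to +0.0017 |
| 1% / 10% | 438–439 | 72 | 87 | 2.8–3.3 | −0.0010 to −0.0003 | +0.0036 to +0.0045 |
| 5% / 5% | 2,087–2,091 | 182–184 | 219–222 | 8.2–8.5 | −0.0010 to +0.0004 | +0.0094 to +0.0110 |
| 5% / 10% | 2,088–2,097 | 344–347 | 417–422 | 16 | −0.0018 | +0.0176 to +0.0211 |

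Across all scenarios, stopping at any death changes the mean HR by −0.002 to +0.0004 (at most 0.015 in one simulated trial). Counting the deaths as events raises it by 0.001 to 0.021 (at most 0.067 in one trial). About 95% of the known dead are carried past their death date; in the rest the simulated MACE comes first.

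**The case against.** The strongest reply is that the defect barely matters. That stands for the post-death time: even 422 patient-years is under 1% of the planned 14,000 × 3.5 = 49,000, and the HR hardly moves. MACE-4 includes CV death, so the Step 1 hazard already carries an average CV-death risk for these patients. It does not use the deaths actually observed.

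A second reply is that stopping at a death of unknown cause treats a possible CV death as uninformative censoring. That is right, and it is why the stop should not be adopted alone.

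Three stronger readings are tempting, and the documents do not support them.

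- *The plan's 1% per year loss rate gives the number of ignored deaths.* It does not. Protocol 10.7.5 and SAP 4.3 reserve lost to follow-up for patients whose vital status stays unknown, so a patient found dead is by definition not in that group. The plan gives no rate for patients who leave and are later traced, and no tracing or mortality rate.
- *The effect is large if all the deaths fall on active.* Splitting 1,620 events 744 v 876 (ratio 0.849), 12 or 24 extra active-arm events give 756/876 = 0.863 or 768/876 = 0.877. That measures a worst-case classification, not the missing stop. With no arm difference, the chance that all 12 fall on active is 0.5¹² ≈ 0.0002. For 768 v 876 the upper 95% limit is 0.877 × exp(1.96 × √(1/768 + 1/876)) ≈ 0.97, still below 1.
- *The deaths vanish from the report.* They do not. SAP 9 has final survival status summarised for the full analysis set and listed, so an imbalance could be seen there. They are missing only from these two analyses.

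**Conclusion.** The gap is real on the text and minor in effect. In Step 2 the only death that ends simulated follow-up is one labelled non-CV, and search-only deaths have no label. Most of those patients therefore stay at risk after a known death, and a possible CV death is ignored. The total in 15.2.3 has the same gap but is only descriptive.

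The sizes rest on assumed dropout, mortality and complete tracing, with equal mortality in both arms: about 0.002 or less on the HR for post-death time, and about 0.001–0.021 when the deaths count as events. Larger shifts would need deaths that are unequal between arms. The primary test, its alpha and the event target are untouched. If the sponsor in practice assigns a non-CV cause to some of these deaths, Step 2 would stop at them, but the SAP does not say so. The text available for review does not include SAP Section 18, so the conclusion is about Appendix 6 as written.

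**What to change.** 1. In Appendix 6, Step 2, end simulated follow-up at the calendar date or the date of death from any cause, including deaths found only in the vital-status search.
2. Pair this with one added run in which search-found deaths of unknown cause count as MACE-4 on the death date, and state how such deaths are classed. The stop and the added run should be adopted together.
3. In SAP 15.2.3, end the patient-years lost at the same death date.

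This costs a few sentences and one extra run of existing code, using data already planned for collection. The sensitivity result may look slightly less favourable. Because tracing is limited by legal and ethical bounds, the added run should be reported with the number of patients traced in each arm. The wording should be settled before database lock and unblinding, the point by which SAP 5.3 says the plan is final.

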8. STATISTICAL CONSIDERATIONS

8.1. Sample Size

This event-driven study is designed to provide at least 90% power to detect an approximate 15% relative risk reduction in hazard ratio corresponding to the primary composite MACE endpoint (CV death, nonfatal MI, nonfatal stroke, or coronary revascularization) at an overall study significance level (alpha) of 0.05. There are no interim efficacy analyses.

A statistical relationship between on-treatment LDL-C differences between the bempedoic acid group and the placebo group and CV event risk reduction is used to derive the postulated treatment effect of 15% stated above. Assuming a 3.59% annual event rate in the placebo group, a minimum of 1620 primary composite MACE events are needed.

The average follow up duration for all patients is estimated to be approximately 42 months (~3.5 years), with an enrollment phase of approximately 33 months, a minimum follow up duration of 24 months (2 years), and a lost-to-follow-up (LTFU) rate of 1% per year. Based on these assumptions, approximately 14,000 patients (approximately 7000 in the bempedoic acid group and 7000 in the placebo group) were randomized into the study to achieve 1620 patients experiencing an adjudicated primary endpoint event.

It is expected that at least 50% of the 1620 patients experiencing an adjudicated primary 4 component MACE (810 patients) will experience an adjudicated 3 component MACE (CV death, nonfatal MI, or nonfatal stroke). Therefore, the study will not stop until at least 1620 patients have experienced an adjudicated primary MACE endpoint, with 810 patients experiencing an adjudicated 3 component MACE, and a minimum of 24 months (2 years) have elapsed since the last patient was randomized.

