8.3. Multiplicity

There are one primary and six key secondary efficacy endpoints of interest for statistical testing in this study. A gatekeeping or hierarchical approach is used to test the primary efficacy endpoint and then key secondary efficacy endpoints sequentially to preserve the study-wise Type I error rate at 5%. For each endpoint, the null hypothesis is that of no difference between bempedoic acid and placebo groups, and the order for the hierarchical testing is:

1. time to first occurrence of MACE (CV death, nonfatal MI, nonfatal stroke, or coronary revascularization; primary 4-component MACE)
2. time to first occurrence of the composite endpoint of CV death, nonfatal MI, or nonfatal stroke (3 component MACE)
3. time to first occurrence of fatal or nonfatal MI
4. time to first occurrence of coronary revascularization

5. time to first occurrence of fatal or nonfatal stroke
6. time to CV death
7. time to all-cause mortality

For the final analysis of the differences between bempedoic acid and placebo, each hypothesis in this hierarchical order will be tested at a two-sided significance level of 0.05. Statistical significance at each step is required in order to test the next hypothesis. If any of the endpoints does not reach statistical significance, p-values for subsequent endpoints will be reported for information only.

For other efficacy and safety endpoints, a nominal p-value may be reported for information only.

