15.2.4. Sensitivity Analyses of Primary Efficacy Endpoint

In the primary analysis, censoring is assumed to be uninformative, i.e., patients who were censored share a common hazard function as those who were not censored in the same treatment group. However, there is a key difference between them as the censored patients also by definition stopped the treatment, while the majority of those remained on-study were still on-treatment. To evaluate the potential impact, two sensitivity analyses will be performed:

- Multiple imputation analysis: the hazard function for patients after censoring is assumed to be the same as those patients who were assigned the same treatment, had stopped treatment but remained in the study follow-up longer. The data from those patients with follow-up will be used as the model for imputation of the time to events for the censored patients.
- Tipping point (TP) analyses: The goal of this analysis is to explore the plausibility of unobserved data assumptions under which the conclusions change. Unlike the standard multiple imputation analysis, the censored patients in the active treatment group are allowed to have the same or even worse outcome than those in the placebo group. A range of assumed hazard ratios (vs placebo) will be used to evaluate when the estimated treatment effect starts to “tip”, i.e., becoming in favor of the placebo.

The details of the analyses are specified in Appendix 6.

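### The tipping-point analysis does not count loss of significance as a tip, and its grid stops at an imputed hazard ratio of 1.10

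*SAP*

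**What the plan says.** SAP Section 15.2.4 plans a tipping-point analysis of the primary MACE-4 endpoint and states its purpose: "The goal of this analysis is to explore the plausibility of unobserved data assumptions under which the conclusions change". The same paragraph defines tipping as the estimated treatment effect "becoming in favor of the placebo".

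Appendix 6, Step 2, sets the assumption to be varied, which is the active-versus-placebo hazard ratio for censored patients after they stop treatment: "a range of values (from hazard ratios of 1.00 to 1.10 in 0.01 increment) will be used". That is 11 values. The text gives no rule for continuing if none of them tips. For each censored patient "a time to event is simulated from the fitted model in Step 1, and it is added to the date of last dose", and follow-up then ends at a calendar date (redacted in the public copy) or at non-CV death. Step 3 fits a Cox model to each simulated dataset and pools the log hazard ratios by Rubin's rules.

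The conclusion being stress-tested is set in SAP Section 8.3: "each hypothesis in this hierarchical order will be tested at a two-sided significance level of 0.05".

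**The concern.** The stated purpose and the stated rule do not agree. The trial's conclusion on the primary endpoint is significance at two-sided 0.05, and the six key secondary tests depend on it. That conclusion changes when the pooled upper confidence limit reaches 1. The SAP recognises a tip only later, when the point estimate itself crosses 1.

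Two consequences follow:

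- A fragile result could be described as not tipping although its pooled interval already includes 1 within the grid.
- A robust result cannot be shown to be robust. The grid ends at 1.10, so the value at which the conclusion would change is never found and the reader cannot judge how extreme it is.

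**Working it through.** **Inputs from the documents.** SAP 8.1: 1,620 events, hazard ratio (HR) 0.85, power at least 90%, placebo rate 3.59%/yr, loss to follow-up 1%/yr, enrolment 33 months, average follow-up 42 months. SAP 4.1: about 7,000 per arm, 1:1. SAP 8.3: two-sided 0.05.

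**The plan's own figure.** Schoenfeld: 4(1.960 + 1.282)² / (ln 0.85)² = 1,592 events. Freedman gives 1,599. Power at 1,620 events is 90.5%. The plan's 1,620 is reproduced.

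**How far a significant result is from the SAP's tip.**

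- Largest significant HR: exp(−1.96 × 2/√1620) = exp(−0.0974) = 0.907.
- With log-HR weighting, the imputed share *w* of final events needed for an imputed HR of 1.10 to bring the pooled HR to 1 solves (1 − w) ln(HR) + w ln(1.10) = 0.
- From 0.907: w = 0.0974/(0.0974 + 0.0953) = 51%.
- From 0.85: w = 0.1625/(0.1625 + 0.0953) = 63%.
- Weighting by active-arm person-time, HR(1 − s) + 1.10s = 1 gives s = 48% from 0.907 and 0.15/0.25 = 60% from 0.85. At the planned 1%/yr loss, the lost share of active-arm follow-up is about 1.8%.

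**Appendix 6 as written (simulated time added to last dose).** The simulation used 14,000 patients and a cut-off at 1,620 events and at least 24 months after the last randomization. It ran nine scenarios of 200 trials with 20 imputations (the SAP uses 100). True HR was 0.85 or 0.88.

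These assumptions are not in the documents: IMP discontinuation 5–20%/yr, loss of 5%/yr in some scenarios, non-CV death 1%/yr, the redacted date equal to the event-driven cut-off, and treatment effect unchanged after stopping IMP. The Ukraine censoring rule is not modelled.

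- Imputed events at HR 1.00: 175 to 687. At HR 1.10 they make up 10–31% of all events, against the 51% needed.
- Of 1,491 initially significant trials, none had a pooled HR of 1.00 or more at imputed HR 1.10 (highest 0.974). The smallest imputed HR at which any estimate crossed 1 was 1.18.
- In 594 of the 1,491 (40%, pooled over all nine scenarios) the pooled upper limit reached 1 inside the grid. The SAP's definition labels none of these a tip.

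At true HR 0.85 and 1%/yr loss:

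| Assumed IMP discontinuation | Significance lost by 1.10 | Same, observed upper limit 0.97–1.00 | Median imputed HR at loss, remaining trials |
|---|---|---|---|
| 5%/yr | 8% | 54% | 1.59 |
| 10%/yr | 16% | 91% | 1.35 |
| 20%/yr | 39% | 100% | 1.20 |

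Separately coded, smaller simulations gave 5–8%, 21–28% and 40–41% for the second column. None had a pooled HR of 1 or more at 1.10 (highest 0.962 and 0.958).

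**Imputing from the censoring date instead.** An exponential expected-value model with 1%/yr loss, 42 months' mean follow-up and an approximate Rubin variance gives:

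| Observed HR | Upper limit at imputed 1.00 → 1.10 | Significance lost at | Estimate reaches 1 at |
|---|---|---|---|
| 0.85 | 0.9436 → 0.9455 | 4.4 | 15.5 |
| 0.87 | 0.9648 → 0.9667 | 3.0 | 12.3 |
| 0.90 | 0.9965 → 0.9985 | 1.18 | 8.6 |

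The 0.90 row is sensitive. With a minimum follow-up of exactly 24 months (mean 24 + 33/2 = 40.5 months), significance is lost at about 1.10. At observed HR 0.85 and assumed loss of 2, 5 and 10%/yr, it is lost at 2.5, 1.47 and 1.15, all beyond the grid. Simulation of this reading at 1%/yr loss gave about 35 imputed events and a median tipping HR of about 5.5.

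**The case against.** - **The in-grid share depends on the literal last-dose wording.** Section 15.2.4 speaks of the hazard after censoring, whereas Appendix 6 starts the clock at the last dose and so overwrites observed event-free follow-up. That conflict is a separate matter. From the censoring date, the share losing significance inside the grid is only about 2–4% at true HR 0.85 (0–8% at 0.88) with 1%/yr loss. This stands and limits the first consequence. It worsens the second, because the tipping value then lies even further beyond 1.10.
- **The pooled 40% reflects chosen scenarios.** This also stands. The 8%, 16% and 39% at the design effect and loss rate are the better summary, and they still rest on an undocumented discontinuation rate.
- **Nothing is hidden.** Rubin pooling yields an interval at each grid value, so a careful reader could see significance disappear. That is true, but the pre-specified rule would not call it a tip, and it gives no information above 1.10.
- **A bounded grid is a judgement about plausibility.** A ratio of 1.00 already removes all benefit in the imputed follow-up, and no document suggests patients fare more than 10% worse than placebo after stopping. That makes the grid interpretable, but not a search for the point where the conclusion changes. SAP 5.3 permits further analyses marked ad hoc, which carry less weight than a pre-specified extension.
- **Part of the text is unavailable.** The calendar date in Appendix 6 is redacted, and Section 18.4 (further sensitivity analyses) is listed but not in the public copy. The statement that no extension rule exists applies to the visible text.

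**Conclusion.** The concern holds. As written, the rule cannot meet its own stated goal. The defined tip is practically unreachable for a significant result: about half of all final events would have to be imputed even from a borderline HR of 0.907. That does not depend on the simulation assumptions, and no simulated significant trial tipped.

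How often significance is lost inside the grid without being labelled does depend on assumptions. It is 8–39% at true HR 0.85 under the last-dose wording with 5–20%/yr discontinuation, and about 2–4% if imputation starts at censoring. Where significance survives to 1.10, the value at which it would be lost is not found under either reading. The primary test, its alpha and the testing hierarchy are unaffected; this concerns the sensitivity analysis only. It should be corrected before database lock.

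**What to change.** In SAP 15.2.4, define the tipping point as the smallest imputed hazard ratio at which the pooled (Rubin) upper 95% confidence limit reaches 1.00. Report separately the value at which the pooled hazard ratio itself reaches 1.00.

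In Appendix 6, keep 1.00 to 1.10 in steps of 0.01, then continue (for example in steps of 0.05) until the tip occurs or a pre-stated implausible bound (for example 3.0) is reached. Report the tipping value, or that it was not reached up to the bound. With imputation from the censoring date the tip may lie above 3.0, as the 4.4 and 5.5 above show. Not reached up to 3.0 would still say far more about robustness than not reached up to 1.10.

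The cost is SAP wording and extra simulation runs before database lock. No new data are needed.
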